Universal health and wellbeing promotion targeting the general population, including those with compromised wellbeing, recurrent common mental health problems and general low levels of mastery, may prove highly beneficial. As indicated by the prevention paradox, modest improvement in individuals may have a powerful impact at the population level. Figure 1 illustrates how small to moderate individual effect sizes (i.e., $d=0.3$) will have major effects on population level (i.e., reduce a prevalence of 8% by 3.5%). This example implies that in a population of 1 million, a universal intervention moving the distribution 0.3 sd in the positive direction would result in 35,000 fewer disease cases.

[figure not shown]

Figure 1. The population effect of public health measures with the effect size of Cohen’s $d=0.3$.

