1.3 Research questions and hypotheses, theoretical approach and methodology

Main hypothesis: The web-based intervention 5WaysA will improve wellbeing and mastery and hence provide the municipalities with an effective measure for mental health promotion.

Research questions:

1. *To what extent does participation in the web-based 5WaysA intervention lead to improved wellbeing, mental health and mastery in the general population?*
2. *To what extent are the effects short-term and long-term (i.e., 10 weeks and 12 months)?*
3. *What mechanisms explain potential improvements in wellbeing?*
 - a) *For whom is this intervention effective (i.e., is the effect moderated by e.g. gender, age, education)?*
 - b) *What mechanisms (e.g., regular practicing of 5Ways actions, increased social activity or support) explain intervention effects?*

Sample: The sample consists of participants from the general population in Norwegian municipalities. A cooperation with public health alliances in the Viken and Trøndelag regions, as well as Sunne kommuner, the Norwegian WHO Healthy Cities network, has already been established. Public health coordinators in all of the municipalities will be involved in recruitment. Invitations to participate will be distributed via emails, the municipalities' web sites, social media, local newspapers, citizen panels (e.g., *Innbyggerpanelet* in Bærum) and related means. We plan to recruit a minimum of 1500 participants. The participants will be randomized to either an intervention group ($n=750$) or one of two wait-list control groups (active control group, $n=375$) (passive control group, $n=375$), receiving the intervention five months later. Citizen panels, like the one we will recruit from in Bærum, invites inhabitants to contribute with experiences and opinions about their lives in the municipality and about municipal services. The citizens' opinions contribute to new understandings, new ideas, innovative solutions and development. All participating regions and networks involved in our study have a strong tradition for involving the citizens in their work and have implemented wellbeing in their regional strategies.

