Design: The design is a randomized controlled trial (RCT), with one intervention group and two wait-list control groups. The goal with this design is to demonstrate the initial efficacy and feasibility of the 10 week 5WaysA intervention. We choose an RCT with two wait-list control groups, where one wait-list is writing activity log and the other is passive while waiting. We add the active control because we are aware of the limitations in passive wait-list control group conditions. However, both wait-list control groups will know they are waiting for an intervention, which can in turn produce demand characteristics. The intervention group will receive the 5WaysA intervention within a few weeks after announcing their interest in participating in the study. The wait-list control groups will receive the 5WaysA intervention 5 months after the intervention group had the intervention. The active wait-list control group is encouraged to write an activity log every week. The passive wait-list control group is not getting any tasks while they are waiting, other than a questionnaire. Figure 2 shows the time line for recruiting, randomizing and the schedule for intervention and measurement points (M).

Power analysis: We assume that we can recruit a minimum of 1500 participants, but high drop-out is expected. An a priori power analysis was conducted using G*Power3[40] to test the interaction effect in a mixed ANOVA, using a two-tailed test, assuming a small effect size ($f = .10$), and an alpha of .05. The assumed effect size ($f=0.1$) was chosen as it is of the same magnitude (lower bound) as has been reported by other universal interventions with wellbeing as the outcome measure[41]. The result showed that if we attained a total sample of 750 participants at our second measurement point (attrition of 50 %), we would have power of .999 to detect a group by time interaction. The high level of statistical power will enable us to investigate both moderators and mediators.

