Procedures: The webinar will be a live lecture with an independent trained facilitator. Questionnaires will be administrated and distributed by the project manager using the Nettskjema and Services for sensitive data (TSD) tools. The measurements for the intervention group will be conducted when the participants register to participate (baseline, just before the main webinar) (M1), at the booster session webinar one months after the completed main webinar (M2), 10 weeks after the main webinar (M3), five months after the main webinar (when control groups are starting) (M4) and 12 months after the intervention is completed (M5). Control groups will be measured when the participants register to participate (baseline, just before the main webinar) (M1), when the interventions group has completed the intervention (M2), when they start the intervention (main webinar) (M3), at the booster session one months after the completed main webinar (M4), ten weeks after the main webinar (M5) and 12 months after the intervention is completed (M6)

Data analysis: The effect analysis will involve a comparison of self-reported wellbeing at different measurement points, using a two-way mixed measures ANOVA. In addition, we will run a longitudinal analysis using linear mixed (multilevel) models on the data from all five measurement time points. Mixed modelling is a flexible way to handle unbalanced data in case of non-registration and repeated observations. The models allow us to investigate the effects of the intervention and test the hypotheses of group and individual development in wellbeing while controlling for both stable and time-varying covariates.

Ethics and privacy: All the participants will receive a letter of information about the study, also specifying the requirements of The Regional Committees for Health Research Ethics (REK). A written consent from all participants in all groups will be obtained. All sensitive personal information will be handled according to GDPR requirements. Data will be stored and analyzed under the Services for sensitive data (TSD) at UiO. The study will be preregistered in Open Science Network/Clinicaltrials.gov.

Risks: There is a low probability that this study leads to any disadvantage, damage or risk for the participants. The activities they are encouraged to engage in are universal, general and easy to adapt to differences in age, culture, socioeconomic background and state of health.

| Risk | Consequences | Planned measures |

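### Power allows for 50% attrition, but no planned analysis tests dropout that depends on unseen outcomes and differs between arms

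*Combined protocol and SAP*

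**What the plan says.** All of this is in section 1.3 of the combined protocol and SAP, except the risk table that closes part 1.

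- **Sample.** "We plan to recruit a minimum of 1500 participants". Half (750) go to the intervention and the rest to "one of two wait-list control groups (active control group, $n=375$) (passive control group, $n=375$), receiving the intervention five months later".
- **Power analysis.** "We assume that we can recruit a minimum of 1500 participants, but high drop-out is expected". The calculation is for a group-by-time interaction, "using a two-tailed test, assuming a small effect size ($f = .10$), and an alpha of .05". The claim is conditional: "if we attained a total sample of 750 participants at our second measurement point (attrition of 50" %), then "we would have power of .999 to detect a group by time interaction".
- **Data analysis.** The effect analysis is a two-way mixed ANOVA on self-reported wellbeing. Linear mixed models come in addition. One sentence bears on missing data: "Mixed modelling is a flexible way to handle unbalanced data in case of non-registration and repeated observations".
- **Procedures.** Intervention M2 is taken at the booster webinar, about one month in, and M3 at 10 weeks. Control M2 is taken when the intervention group has finished, so it pairs with intervention M3.
- **Risk table.** Dropout appears only as something that a short questionnaire, checked by the user panel, should limit.

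The available text gives no missing-data assumption, analysis set, imputation, comparison of dropouts with completers, or sensitivity analysis for dropout.

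**The concern.** When up to half the outcomes may be unobserved, the missing-data assumption carries about as much weight as the data. The two planned analyses make different assumptions, and the plan states neither. A standard mixed ANOVA drops anyone who lacks a compared measurement. The likelihood-based mixed model is weaker in what it demands: dropout may depend on anything observed and modelled. Neither is protected if people stop answering because of how they are doing at the missed measurement, and if this happens to a different degree in the two arms.

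The protocol gives reasons to expect a difference. The intervention arm has webinars and twice-weekly SMS tasks, and its M2 is tied to attending the booster session. Active controls keep a weekly log. Passive controls have only a questionnaire. Both control arms are still waiting for the course, which may keep them responding.

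At stake is the use made of the result. Section 1.1 illustrates the public-health case by saying that "a universal intervention moving the distribution 0.3 sd in the positive direction would result in 35,000 fewer disease cases". A figure of that kind applies to everyone offered the intervention, including those who drift away.

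**Working it through.** **1. The plan's own figure.** Inputs from the Power analysis: N = 750, f = 0.10, alpha .05. The number of groups k, measurements m and correlation ρ are not stated; I take k = 3, m = 2, ρ = 0.5. With the G*Power within-between interaction formula, λ = N·f²·m/(1−ρ) = 750 × 0.01 × 2/0.5 = 30, with df 2 and 747. Power is 0.9992 (0.9998 for k = 2), so .999 reproduces. With m = 2 it stays within 2 points for ρ of 0.3 or more, but falls to 0.943 (k = 3) or 0.972 (k = 2) at ρ = 0. Power concerns precision and says nothing about bias.

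**2. Effect size for illustration.** I use 0.20 SD: d = 2f for two equal groups, and the low end of the 0.2–0.3 that section 1.1 cites. It is not the effect to which .999 attaches. A plain comparison of two means at 0.20 SD with 375 per group has power 0.78.

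**3. Bias.** Let p be the fraction missing in an arm and δ the amount by which its dropouts do worse than the MAR model supposes. Then

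all-randomised effect = MAR estimate − (p_int·δ_int − p_ctl·δ_ctl).

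With p = 0.5 in both arms (assumed) this is the MAR estimate − 0.5·delta, where delta = δ_int − δ_ctl. If intervention dropouts end up no better than controls, delta equals the estimate: 0.20 becomes 0.20 − 0.5 × 0.20 = 0.10. The 0.27 cited for technology-assisted interventions becomes 0.135.

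**4. Tipping points.** With 375 v 375 completers (controls pooled, even attrition), SE = √[(1/375 + 1/375)(1 − ρ²)], ignoring added imputation variance.

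| Assumed ρ | SE | Lower 95% limit for 0.20 | Delta that brings limit to zero | Delta that removes effect |
|---|---|---|---|---|
| .5 | .063 | .20 − 1.96 × .0632 = .076 | .076/0.5 = 0.15 | .20/0.5 = 0.40 |
| .7 | .052 | .20 − 1.96 × .0522 = .098 | .098/0.5 = 0.20 | 0.40 |

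**5. Simulation.** 750 v 750, no true effect, ρ = 0.5, 2000 runs per row. Retention depends on the person's own change through the stated log-odds per SD. At 0.5, someone 1 SD above average change is retained with probability e^0.5/(1 + e^0.5) = 62%, against 38% at 1 SD below. The change-score comparison in completers equals the two-time-point ANOVA interaction. The baseline-adjusted analysis stands in for a MAR model. Cells show the mean false effect in SD and the rejection rate.

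| Retention depends on | Retained, int/ctl | Change score | Baseline-adjusted |
|---|---|---|---|
| nothing | 50/50 | 0.00, 5% | 0.00, 5% |
| own change, 0.25, intervention only | 50/50 | 0.12, 38% | 0.09, 32% |
| own change, 0.5, intervention only | 50/50 | 0.24, 91% | 0.18, 82% |
| own change, 0.5 intervention, 0.25 control | 50/50 | 0.12, 36% | 0.09, 29% |
| own change, 0.5, both arms | 50/50 | 0.00, 4% | 0.00, 5% |
| own change, 0.5, both arms | 40/60 | 0.09, 24% | 0.07, 19% |
| observed baseline, 0.5, intervention only | 50/50 | −0.12, 35% | 0.00, 5% |

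The last row shows that the ANOVA can be biased where the MAR analysis is not. The other rows show that neither is safe when unseen outcomes drive dropout differently by arm.

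**The case against.** The strongest reply is that mixed models are a standard response to dropout, that MAR allows dropout to depend on observed values, and that the intervention arm's one-month measurement captures some early lack of benefit among those who answer it. That stands. It is why the mixed model should lead. It does not reach people who are lost before M2 or whose outcome changes after it.

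A second reply is that bias needs a difference between arms. That also stands: equal informative dropout with equal retention gave none. A reader might infer that the problem arises in the intervention arm alone, because controls have nothing to abandon. The Design paragraph does not support this, since half of the controls (375 of 750) are asked to keep a weekly log.

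Three other strong readings go too far. The plan does not assume that dropout is unrelated to outcome; the mixed model's requirement is weaker than that. The 50% is a power scenario at the second measurement, which is one month for the intervention arm and about 10 weeks for controls; it is not a forecast for each arm at 10 weeks. And the Design paragraph sets the goal as early evidence of efficacy and feasibility, so a population-level effect is an ambition and not the designated estimate.

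**Conclusion.** The concern holds as a gap in the analysis plan. It is not a demonstration that the result will be biased. If half of each arm is missing at 10 weeks, a differential of about 0.15 to 0.20 SD between what intervention dropouts experience and what the model supposes brings the lower limit of a 0.20 SD estimate to zero, and 0.40 SD removes the effect. Under arm-specific dropout of moderate strength, the simulated false effects (0.18 to 0.24 SD) are as large as that estimate.

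These figures rest on assumed correlations, an assumed 50% per arm at 10 weeks, and assumed dropout mechanisms, none of which the documents give. The bias could also run the other way if those who feel better stop answering. A reader might infer that a positive finding would be produced entirely by those who stayed. The documents cannot show that; they show only that nothing planned would tell the two situations apart. The change is worth making before the data are seen because it is cheap and alters what can be concluded.

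**What to change.** In Data analysis (section 1.3):

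1. Make the linear mixed model on all randomised participants, rather than the ANOVA, the main estimate for the 10-week comparison (intervention M3 v control M2), and state its MAR assumption. The plan names no primary time point. Ten weeks is named in research question 2 and precedes the controls' course.
2. Report dropout by arm at each measurement.
3. Pre-specify jump-to-reference multiple imputation, in which intervention participants who stop responding follow the wait-list mean from then on. Name the reference group, the variance method, and how the intervention arm's M2 enters, as controls have no one-month measurement.
4. Pre-specify a delta-adjusted tipping-point analysis, for example subtracting 0 to 0.5 SD in 0.1 SD steps from imputed intervention values. Report the delta at which the confidence interval reaches zero, and judge whether it is plausible.
5. Use the SMS replies already collected as auxiliary data in the intervention arm. The documents do not say that webinar attendance is recorded, so nothing here relies on it.
6. Do not call the effect robust because the reference-based estimate keeps its sign. That method mainly shrinks the estimate towards zero, so the sign can hardly change.
7. Show the reference-based estimate beside the MAR estimate in any population-impact statement.

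The cost is a paragraph in the plan and a few days of analysis, with no new data. The downside is that the headline effect may look less favourable.

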2.1 Potential impact of the proposed research

According to the Norwegian Public Health Act, municipalities are obliged to work systematically with health promotion and illness prevention[48]. An investigation conducted by the Office of the Auditor General of Norway in 2015 revealed that mental ill health is the largest health challenge for Norwegian municipalities, that there is too little focus on systematic health promotion, and that the lack of research on evidence based interventions makes it difficult to make decisions and choose actions[49]. In trying to fulfil the law requirements, the Norwegian government and municipalities continuously search for “what works” when planning interventions aiming to promote health and mastery. Low-cost and evidence-based health promoting public health tools, are urgently needed in the Norwegian municipalities.

There is similarly a need for high quality intervention studies, using randomised controlled trials and multiple assessments, so that causality can be established. There is also an urgent need for more research on web-based interventions, especially in the light of the pandemic of Covid-19 and potential future crises that require social distancing. This study will improve the knowledge foundation needed for making priorities and decisions regarding effective health promotive interventions. In addition, the project has the potential to become an important and highly warranted bridge-builder between academic research and the practice field in the municipalities. The study will highlight core barriers that exist in these types of cooperation, but also point out the criteria for success when the cooperation is working, and useful research is produced.

Increasing the general population's wellbeing is essential to keep people healthy, well and able to work. As an overreaching goal this project seeks to find ways to contribute to better health and wellbeing among Norwegians, but also internationally if utilized in other counties. Our study therefore addresses The United Nations' Sustainable Developmental Goals (SDGs) goal #3: "Ensure healthy lives and promote wellbeing for all at all ages". In addition, our study may have the potential to keep people at work/in training and may in this way stimulate to both economic growth and the reduction of social inequalities. Thus, the study also addresses also the UN's SDG #8: "Decent work and economic growth" and SDG #10: "Reduced inequalities".

2.2 Measures for communication and exploitation

Several users and stakeholders are of relevance to this study, including the general population, local politicians and the municipality administrations. Scientific findings will be disseminated through research communication channels like international open access journals in the fields of public health, wellbeing, psychology and internet-based solutions. The results will also be presented at national and international conferences and seminars. Findings from the study will be made available for all interested stakeholders in the municipalities in Norway, the general population, national health authorities and the media. We will use local newspapers, central authorities in the municipalities and local as well as national seminars to spread the results. The NCMH, the research team at PROMENTA Research Centre and The Norwegian Institute of Public Health (NIPH), will actively participate in the communication by publishing on their web-pages to make findings easily available to researchers, authorities, journalists and the public. Newspapers and social media, such as Twitter and Facebook, will be used actively. PROMENTA has a communication unit headed by Sunne kommuner, the Norwegian part of the WHO Healthy Cities Network, with a broad national and international outreach to important stakeholders. Distribution of our findings will also be supported by the information and press departments of at the UiO and the NIPH and distributed via their websites, newsletters and social media to reach a large audience. The NIPH currently has more than 100,000 followers on Facebook and 26,000 on twitter. Web statistics show 30 million page views during the first quarter of 2020.

The NCMH is our main cooperating partner in this project. The council has a special interest in research on universal interventions, targeting the general population. They will also be interested and active in the communication of the results from our study to other municipalities in Norway, in their continuous work advising local decision makers to the promotion of wellbeing and prevention of health problems. The Public Health network in Viken and the Alliance for Public health in Trøndelag will actively communicate the research finding in their networks.

3. Implementation

3.2 Project organisation and management

To ensure sufficient time for data collection, the PhD project is scheduled over 4 years, starting in January 2021, and ending in December 2024.

| Tasks | 2021 | | | | 2022 | | | | 2023 | | | | 2024 | | | | |
|---|------|----|----|----|------|----|----|----|------|----|----|----|------|----|----|----|----|
| | Q4 | Q1 | Q2 | Q3 | Q4 |
| Work Package (WP)1: Preplanning | | | | | | | | | | | | | | | | | |
| User involvement | | | | | | | | | | | | | | | | | |
| Ethics approval | | | | | | | | | | | | | | | | | |
| Pilot | | | | | | | | | | | | | | | | | |
| WP 2: Intervention and measures | | | | | | | | | | | | | | | | | |
| Recruitment | | | | | | | | | | | | | | | | | |
| Intervention to intervention group | | | | | | | | | | | | | | | | | |
| Intervention to control groups | | | | | | | | | | | | | | | | | |
| Questionnaire/measuring points | | | | | | | | | | | | | | | | | |
| WP 3: Analyses short-/long- time | | | | | | | | | | | | | | | | | |
| Between group comparison | | | | | | | | | | | | | | | | | |
| Intervention group 3 months | | | | | | | | | | | | | | | | | |
| Control groups 3 months | | | | | | | | | | | | | | | | | |
| Intervention group 12 months | | | | | | | | | | | | | | | | | |
| Control groups 12 months | | | | | | | | | | | | | | | | | |
| Mediators and moderators | | | | | | | | | | | | | | | | | |
| WP 4: Dissemination | | | | | | | | | | | | | | | | | |
| First article | | | | | | | | | | | | | | | | | |
| Second article | | | | | | | | | | | | | | | | | |
| Third article | | | | | | | | | | | | | | | | | |
| Thesis work and submission | | | | | | | | | | | | | | | | | |
| Dissemination stakeholders | | | | | | | | | | | | | | | | | |
| Dissemination to public and the media | | | | | | | | | | | | | | | | | |

